### 11.3 Analysis of Demographic and Pretreatment Variables

Descriptive statistics will be generated for demographic and pretreatment variables for Randomized Population and other analysis populations which will be defined in detail in the Statistical Analysis Plan.

Medical history terms will be coded using the Medical Dictionary for Regulatory Activities (MedDRA) and summarized by SOC and Preferred Term for each treatment group based on the safety population.

#### **11.4 Disposition of Subjects**

The number and percentage of subjects randomized and included in each analysis population will be summarized by treatment and overall. Reasons for excluding subjects from the analysis populations will be presented in a by-subject listing.

The number of randomized subjects who completed the study, discontinued early from study drug, completed or discontinued from the study, and reasons for discontinuation will be summarized by treatment group and overall.

#### **11.5 Missing Data**

It is expected that few subjects will discontinue Follow-Up. The reasons for any missing data will be summarized by treatment arm. Missing Hb values will be imputed using last observation carried forward (LOCF).

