A 16-week, open-label, multicenter, Phase 2 trial evaluated vadadustat in 94 subjects receiving chronic hemodialysis previously maintained on epoetin alfa and IV iron form the 3 months prior to Screening (Study AKB-6548-CI-0011 [CI-0011]). Subjects were assigned to one of three vadadustat dose cohorts: 300 mg daily, 450 mg daily, or 450 mg three times a week (TIW). Dosing was fixed for the first 8 weeks; for the subsequent 8 weeks dose was adjusted from 150 to 600 mg according to Hb response based upon a dose adjustment algorithm. Sixty-nine of the 94 subjects completed the study. The primary endpoint was the mean Hb concentration change from pre-treatment average (Screening Visit 1, Screening Visit 2, and Baseline Visit) to mid-study (Weeks 7 to 8) and end-of-study (Weeks 15 to 16) and was analyzed using observed Hb values (no imputation for missing data). No statistically significant mean change in Hb from pre-treatment average was observed for either of the two time points for any of the three treatment groups.

Among subjects randomized to an initial dose of 300 mg daily, 450 mg daily, or 450 mg TIW, 0% (0 of 30), 3% (1 of 33), and 19% (6 of 31) of subjects withdrew from the study due to worsening anemia, respectively. In a sensitivity analysis using last observation carried forward (LOCF) for the primary efficacy endpoint, no significant mean change in Hb from pre-treatment levels was observed in the 300 mg daily dosing group. At Weeks 15 to 16, modest, statistically significant mean decreases were observed in the 450 mg daily and 450 mg TIW dosing groups.

In a post-hoc univariate analysis of baseline characteristics, higher pre-baseline epoetin alfa dose was associated with a decrease in mean Hb at Weeks 7 to 8 and Weeks 15 to 16 in the dosing cohorts. Subjects who discontinued the study due to worsening anemia had a higher mean pre-

baseline epoetin alfa dose compared with subjects who discontinued due to other reasons or subjects who completed the study.

Based on Phase 1 and Phase 2 study results, vadadustat appears to be a suitable candidate for continued development as a treatment for anemia in patients with CKD.

In the ongoing global Phase 3 and Japanese Phase 3 clinical studies, over 7000 subjects are planned to be treated with vadadustat or comparator.

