#### 5.3.2 Key Secondary Endpoints

- Proportion of subjects with Hb values within the target range (10.0 to 11.0 g/dL, inclusive) at the primary evaluation period (Weeks 10 to 12)
- For subjects who transitioned to TIW vadadustat dosing, mean change in Hb from primary evaluation period (average Hb from Weeks 10 to 12) to the secondary evaluation period (average Hb from Weeks 18 to 20)

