#### 5.3.2.1 Other Secondary Endpoints

- Mean change in Hb between Baseline (average pretreatment Hb) and the secondary evaluation period (average Hb from Weeks 18 to 20)
- Proportion of subjects with Hb values within the target range (10.0 to 11.0 g/dL, inclusive) at the secondary evaluation period (Weeks 18 to 20)
- For subjects who transitioned to TIW vadadustat dosing, proportion of subjects with Hb values within the target range (10.0 to 11.0 g/dL, inclusive) at the secondary evaluation period (Weeks 18 to 20)
- Proportion of subjects with a mean increase in Hb from Baseline to the primary evaluation period  $\geq 0.5$  g/dL (average Hb from Weeks 10 to 12) or with Hb values within the target range (10.0 to 11.0 g/dL, inclusive) at the primary evaluation period (Weeks 10 to 12)
- Proportion of subjects with a mean increase in Hb from Baseline to the secondary evaluation period  $\geq 0.5$  g/dL (average Hb from Weeks 18 to 20) or with Hb values within the target range (10.0 to 11.0 g/dL, inclusive) at the secondary evaluation period (Weeks 18 to 20)
- Intravenous (IV) iron supplementation

- ESA rescue
- RBC transfusion

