### 11.2 Study Analysis Populations

The following analysis populations will be used in this study:

- Randomized population: defined as all randomized subjects. Analyses of this population will be based on the randomized treatment.
- Full Analysis Population (FAS): all subjects in the randomized population who received at least one dose of study drug and had at least one Hb assessment during the primary efficacy evaluation period. Analyses of this population will be based on the randomized treatment.
- Safety Population: all subjects in the randomized population who received at least one dose of study treatment. Analysis of this population will be based on the actual treatment received. Subjects who received in error some vadadustat and some epoetin alfa will be classified by the more frequently received drug.
- Per protocol (PP) population: all randomized subjects who received study drug during the primary evaluation period, had at least one Hb assessment during the primary efficacy evaluation period, received no rescue therapy (with ESA or transfusion) prior to the evaluation period, and had no major protocol deviation affecting the primary endpoint analyses. Major protocol deviations leading to exclusion from the PP population will be specified prior to database lock and recorded in a separate document. Analyses of this population will be based on actual treatment received.

Efficacy analyses will utilize the Randomized, Full Analysis, and PP Populations while safety analyses will utilize the Safety Population.

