AE: adverse event; ALT/SGPT: alanine aminotransferase/serum glutamic pyruvic transaminase; aPTT: activated partial thromboplastin time; AST/SGOT: aspartate aminotransferase/serum glutamic oxaloacetic transaminase; BUN: blood urea nitrogen; CBC: complete blood count; CPK: creatine phosphokinase; CRP: C-reactive protein; ECG: electrocardiogram; EOT: end-of-treatment; EPO: erythropoietin; EQ-5D-5L: EuroQol 5 Dimensions 5 Levels; ESA: erythropoiesis-stimulating agent; HDL: high density lipoprotein; INR: international normalized ratio; IWRS: Interactive Web Response System; LDL: low density lipoprotein; LFT: liver function test; MCH: mean corpuscular hemoglobin; MCHC: mean corpuscular hemoglobin concentration; MCV: mean corpuscular volume; PD: pharmacodynamics; PGI-C: Patient Global Impression of Change; PGI-S: Patient Global Impression of Severity; PK: pharmacokinetic; PTT: partial thromboplastin time; RBC: red blood cell; RDW: red cell distribution width; SF-36v2: 36-Item Short-Form General Health Survey; SV1: Screening visit 1; SV2: Screening visit 2; TIBC: total iron binding capacity; TIW: three times per week; TSAT: transferrin saturation; VEGF: vascular endothelial growth factor; WBC: white blood cell; wks: weeks.

- [a] The Screening Period is a maximum of 28 days in duration and starts at the time the informed consent is signed.
- [b] The Screening Period starts at the time the informed consent is signed and will be a maximum of 28-days in duration. Two Screening visits (SV1 and SV2, with a minimum of 4 days in between) must be performed within the Screening Period and prior to dosing (Baseline/Day 1). A subject may enter the washout period only after all eligibility criteria have been met following SV2. During the washout period, no epoetin alfa will be administered before Baseline/Day 1 for 5 days in the Main study, and 2 days in the ESA hyporesponder parallel study.
- [c] The EOT evaluations will be performed when the Treatment Period (Baseline/Day 1 to Week 20 [Visits 1 to 13]) is completed. Subjects who permanently discontinue study drug for any reason or discontinue prematurely from the study will complete the EOT visit (Visit 14) assessments and will complete the Safety Follow-Up (Visit 15) 4 weeks after Visit 14.
- [d] Eligibility criteria will be reviewed at the SV1, SV2, and Baseline/Day 1.
- [e] Contraception methods will be reviewed at Screening and Baseline/Day 1, as well as throughout the study as needed.

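### LOCF for all missing Hb lets subjects who have stopped study drug count as in target range: at Weeks 10-12 in the Randomized population, at Weeks 18-20 in all three efficacy populations

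*Protocol*

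**What the plan says.** Section 11.5 gives one rule for missing hemoglobin: "Missing Hb values will be imputed using last observation carried forward (LOCF"). It sets out no separate rule for responder endpoints, and it introduces the topic with the expectation "It is expected that few subjects will discontinue Follow-Up".

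The endpoints affected are proportions. The key secondary one (Section 5.3.2) is "Proportion of subjects with Hb values within the target range (10.0 to 11.0 g/dL, inclusive) at the primary evaluation period (Weeks 10 to 12"). The matching later one, an other secondary endpoint (Section 5.3.2.1), is "Proportion of subjects with Hb values within the target range (10.0 to 11.0 g/dL, inclusive) at the secondary evaluation period (Weeks 18 to 20"). Section 5.3.2.1 also has a Weeks 18-20 in-range proportion restricted to subjects who moved to TIW dosing, and two composites (a rise of at least 0.5 g/dL, or in range), one for each period.

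On populations, Section 11.2 states: "Efficacy analyses will utilize the Randomized, Full Analysis, and PP Populations". FAS and PP members must have "had at least one Hb assessment during the primary efficacy evaluation period"; the Randomized population has no such condition.

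On follow-up, Appendix A footnote [c] states: "Subjects who permanently discontinue study drug for any reason or discontinue prematurely from the study will complete the EOT visit (Visit 14) assessments". They then have Visit 15 four weeks later. Neither Section 9.3.5 nor Appendix A schedules a CBC at Visit 15.

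**The concern.** An in-range proportion at Weeks 10-12 or 18-20 is meant to show how many subjects the assigned treatment is holding in target at that time. Under the rule as written, someone who left treatment weeks before can be scored as a success on the strength of an old value.

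The protocol's own background argues against carrying that value forward. Section 6.3 says mean Hb fell promptly, within 2 to 4 weeks, once vadadustat was stopped. Section 8.4.12 says vadadustat subjects then go back to an ESA. So the carried value represents neither the later Hb nor continued success on study drug.

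An in-range last value is easy to have. The Main-study screening range of 8.5-11.0 g/dL contains the whole target range. Subjects moved to TIW dosing had to be in range to make the move (Section 8.4.5.2), so one who stops soon afterwards may well carry a success into Weeks 18-20.

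The expectation of few losses also sits poorly with the earlier 16-week hemodialysis study described in Section 4.2: "Sixty-nine of the 94 subjects completed the study".

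**Working it through.** **Inputs from the protocol (Section 4.2, earlier hemodialysis study)**

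- Groups: 30 + 33 + 31 = 94 subjects; 69 completed.
- Withdrawals for worsening anemia: 0/30 = 0%, 1/33 = 3.0%, 6/31 = 19.4%. These reproduce the stated 0%, 3% and 19%. Total 0 + 1 + 6 = 7.
- Non-completers: 94 - 69 = 25, so 25/94 = 26.6%. Non-completers for other reasons: 25 - 7 = 18.

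**Assumptions (not in the protocol)**

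- d, the proportion with no observed Hb in the window: 5%, 10% or 26.6%.
- q, the share of those subjects whose last Hb is 10.0-11.0 g/dL: 0 to 0.7.
- p, the in-range proportion among subjects observed in the window: 0.50.

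**Formulas**, for a population that keeps the dropouts:

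- LOCF: (1 - d)p + dq
- Dropouts counted as not in range: (1 - d)p
- Observed cases only: p
- LOCF minus not-in-range counting = dq, never negative
- LOCF minus observed cases = d(q - p), either sign

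**Results at p = 0.50**

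| d | Not-in-range counting | LOCF, q = 0 to 0.7 | Excess, dq |
|---|---|---|---|
| 5% | 47.5% | 47.5% to 51.0% | 0 to 3.5 points |
| 10% | 45.0% | 45.0% to 52.0% | 0 to 7.0 points |
| 26.6% | 36.7% | 36.7% to 55.3% | 0 to 18.6 points |

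**Using the earlier study's reasons for leaving.** Set q = 0 for the 7 anemia withdrawals and 0.3 to 0.7 for the other 18.

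- Against not-in-range counting: 18/94 x 0.3 = 5.7 points; 18/94 x 0.7 = 13.4 points.
- Overall q: 18/25 x 0.3 = 0.216; 18/25 x 0.7 = 0.504.
- Against observed cases: 0.266 x (0.216 - 0.50) = -7.6 points; 0.266 x (0.504 - 0.50) = +0.1 points.

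**Between arms.** Suppose d is 26.6% in one arm and 10% in the other. The high-dropout arm gains more only if its q exceeds 0.10/0.266 = 0.38 times the other arm's q.

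- Equal q of 0.5: 13.3 against 5.0 points.
- q of 0.2 in the high-dropout arm and 0.7 in the other: 5.3 against 7.0 points, the reverse order.

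**Where the rule acts**

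| Population | Weeks 10-12 | Weeks 18-20 |
|---|---|---|
| Randomized | exposed | exposed |
| FAS, PP | every member has an observed Hb in the window | exposed |

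**Scale.** The Main study plans 5 vadadustat groups of about 15 (75 subjects) and 2 epoetin groups of about 10 (20 subjects). The standard error of a 40% proportion in 75 is sqrt(0.4 x 0.6/75) = 5.7 points. For a 75-against-20 difference it is sqrt(0.24/75 + 0.24/20) = 12.3 points.

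**The case against.** The strongest reply is that the effect is confined and its direction unknown. Much of that stands.

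- A reader might infer that the key secondary proportion is inflated throughout. It is not. FAS and PP require an observed Hb in Weeks 10-12, so only the Randomized population is exposed there, and the Weeks 18-20 proportions are not key secondary endpoints.
- A reader might infer that the inflation is largest in the arm with more dropouts, or that it favours vadadustat. The protocol gives neither dropout nor last-Hb status by arm, Section 4.2 reports no epoetin arm for the earlier study, and the ranking turns on dq and can reverse.
- LOCF need not flatter vadadustat. In the earlier study (Sections 4.2 and 6.2) observed data showed stable mean Hb, while LOCF showed decreases in the two 450 mg groups. Subjects who leave for worsening anemia carry low values, and hyporesponders, screened at 8.0-10.0 g/dL, would mostly carry below-range values if lost early.
- The 26.6% may not transfer. That study had 8 weeks of fixed dosing, a 600 mg ceiling and a group on TIW dosing from the start, which supplied 6 of the 7 anemia withdrawals. Here doses may rise after 2 weeks and up to 900 mg, and TIW dosing follows success on daily dosing.
- Analysis is descriptive, so no test or error rate is affected. Reasons for missing data are tabulated by arm, and a SAP, not at hand, may add further displays.

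What does not fall away is the rule itself. Section 11.5 fixes LOCF without exception, and in a descriptive study the reported proportions are the result.

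**Conclusion.** The point holds as a flaw in the scoring rule, not as a demonstrated bias towards either arm. As written, Section 11.5 can count subjects who are off study drug as held in range: at Weeks 10-12 in the Randomized population, and at Weeks 18-20 in the Randomized, FAS and PP populations, most plausibly among TIW subjects.

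Against counting them as not in range, the excess is about 6 to 13 points if dropout and its reasons resemble the earlier study. That assumes anemia withdrawals are all out of range and 30-70% of the other last values are in range, and it applies a 16-week dropout rate unadjusted to both periods. At 10% dropout the excess is at most 7 points for q up to 0.7, and it is zero if no last value is in range. Against observed cases the same earlier-study inputs give -7.6 to +0.1 points at p = 0.50.

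The excess can match or exceed the standard error of a pooled vadadustat proportion. Bias in the between-arm comparison cannot be sized or signed from the protocol. The change should be made, since it costs little and removes successes that no Hb in the window supports.

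**What to change.** In Section 11.5, limit LOCF to the mean-change endpoints. For every in-range and composite responder proportion, count a subject with no observed Hb in the evaluation period as not in range. This applies at Weeks 10-12 in the Randomized population and at Weeks 18-20 in the Randomized, FAS and PP populations, including the TIW proportion. Present LOCF and observed-case versions as sensitivity analyses, so the reader sees how far the result depends on the rule.

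The cost is wording in the protocol or SAP and two extra displays; no new data are needed. The downside is that the proportions become somewhat lower, and subjects who leave for unrelated reasons, such as transplant, count as not in range. That penalty falls harder on whichever arm loses more subjects, which is why the observed-case version should stand beside it.

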#### **11.6 Efficacy Analyses**

The primary efficacy endpoint as well as all other secondary endpoints will be summarized using descriptive statistics (means or proportions) by treatment groups and in total, as well as by study visit and/or analysis period as appropriate. Mean values of Hb as well as selected other efficacy parameters will be plotted across study visits/periods by treatment group.

#### **11.7 Safety Analyses**

Safety analyses will be descriptive in nature.

All AEs will be coded using MedDRA. Treatment-emergent and post-treatment AEs will be summarized by SOC and preferred term for each treatment group. AEs will also be summarized by their maximum severity.

Summaries will also be provided for the following types of AEs:

- SAEs
- AEs of Special Interest (See [Section 10.1.3](#), Adverse Events of Special Interest)
- Related AEs, as determined by the investigator
- AEs leading to early discontinuation of study drug

All Hb related safety endpoints will be tabulated for each treatment groups.

Observed values of continuous and categorical parameters and changes from baseline for continuous parameters to each study visit will be summarized descriptively for vital signs and clinical laboratory results. Graphical displays of selected laboratory parameters will also be provided.

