#### **10.3.1 Reporting Period**

The AE reporting period for this study begins from time of randomization and ends at the final protocol-required Safety Follow-Up (Visit 15).

In addition, any SAE that occurs subsequent to the AE reporting period that the investigator assesses as related to the study drug will also be reported as an SAE.

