## 11 DATA ANALYSIS

Data collected throughout the study will be summarized using descriptive statistics and listed in the by-subject listings. Continuous variables will be summarized using number of subjects with mean, standard deviation (SD), median, minimum, and maximum. For categorical variables, the number and percentage of subjects in each category will be tabulated. Summaries will be provided by treatment group within appropriate analysis populations (as defined in Section 11.2, Study Analysis Populations) and by time point/time period, as appropriate.

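### Harms are tabulated as crude percentages although AE reporting ends about four weeks after a permanent stop; if one arm stops more often, its percentages rest on less observation time

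*Protocol*

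**What the plan says.** The primary objective (Section 5.1) covers the safety, as well as the efficacy, of daily vadadustat compared with epoetin alfa.

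- **After a permanent stop.** Appendix A, note [c], says that "Subjects who permanently discontinue study drug for any reason or discontinue prematurely from the study will complete the EOT visit (Visit 14) assessments", and that they "will complete the Safety Follow-Up (Visit 15) 4 weeks after Visit 14". Section 9.3.4 also sends early stoppers to the EOT visit.
- **End of AE reporting.** Section 10.3.1 runs the AE window from randomization to Visit 15. Beyond that, only "any SAE that occurs subsequent to the AE reporting period that the investigator assesses as related to the study drug will also be reported".
- **Hb.** The schedule in Appendix A has a CBC at Visit 14. Visit 15 (Section 9.3.5) has none.
- **Temporary interruption.** Under Section 7.6.2 these subjects stay on the visit schedule to Weeks 20 and 24, so only permanent stops shorten observation.
- **Summary measure.** Section 11 states: "For categorical variables, the number and percentage of subjects in each category will be tabulated". Section 11.7 adds that "Treatment-emergent and post-treatment AEs will be summarized by SOC and preferred term for each treatment group" and has the Hb safety endpoints tabulated by treatment group. Neither section names a measure that uses time at risk.

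**The concern.** A crude percentage counts the weeks after a subject leaves observation as event-free. That does no harm to a between-arm comparison when both arms are observed equally long. Here the length of observation depends on when the subject stops drug. A completer gives 24 weeks of AE data and 20 weeks of scheduled Hb; a Week 6 stopper gives about 6 + 4 = 10 weeks and 6 weeks.

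If stopping differs by arm, AEs, SAEs, AEs of special interest and Hb excursions are all understated in the arm that stops more. All safety analysis is descriptive, so these percentages are likely to be what a reader compares. The distortion is systematic: the additional enrolment that Section 11.1 allows would narrow the random error but leave this gap unchanged.

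**Working it through.** **Arm sizes.** The allocation ratios reproduce the plan's 95 subjects. Low stratum: 40 × 3/8 = 15, 15, and 40 × 2/8 = 10. High stratum: 55 × 3/11 = 15, 15, 15, and 55 × 2/11 = 10. That is 75 on vadadustat and 20 on epoetin alfa. The protocol states no AE rate and no stopping rate for this trial, so the rest depends on assumptions.

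**A range for stopping.** For the earlier 16-week hemodialysis study of vadadustat, Section 4.2 reports: "Sixty-nine of the 94 subjects completed the study". So 25/94 = 26.6% did not complete. As a constant hazard this is −ln(69/94)/16 = 0.0193 per week, or 1 − exp(−20 × 0.0193) = 32% by Week 20. I take 15%, 26.6% and 32% for vadadustat and 5% to 26.6% for epoetin. All are assumptions for this trial.

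**Model.** The event hazard h is constant and the same in both arms; the stopping hazard is l. Follow-up is min(stop time, 20) + c weeks, with c = 4 for AEs and c = 0 for scheduled Hb. The true risk p over full follow-up gives h = −ln(1 − p)/(20 + c). Then

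crude % = 1 − exp(−ch) × [ l/(l+h) × (1 − exp(−20(l+h))) + exp(−20(l+h)) ]

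**Worked case, p = 30%, AEs.** h = 0.3567/24 = 0.01486.

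- 32% stopping, l = 0.0193: mean follow-up 16.6 + 4 = 20.6 weeks; crude 26.1%.
- 5% stopping, l = 0.00256: mean follow-up 19.5 + 4 = 23.5 weeks; crude 29.4%.

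**Results for a 30% risk** (differences taken before rounding):

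| Stopping by Week 20, vadadustat v epoetin | AE, crude % | Difference, points | Scheduled-Hb event, crude % | Difference, points |
|---|---|---|---|---|
| 32% v 5% | 26.1 v 29.4 | −3.4 | 25.2 v 29.3 | −4.1 |
| 26.6% v 10% | 26.8 v 28.8 | −2.1 | 26.0 v 28.6 | −2.5 |
| 15% v 5% | 28.2 v 29.4 | −1.2 | 27.8 v 29.3 | −1.5 |
| 26.6% v 26.6% | 26.8 v 26.8 | 0 | 26.0 v 26.0 | 0 |
| 15% v 26.6% | 28.2 v 26.8 | +1.5 | 27.8 v 26.0 | +1.8 |

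At 32% v 5%, an AE with a 50% risk shows as 43.9% v 49.1% (−5.2 points), and a true hazard ratio of about 1.15 to 1.17 would look like equality. Under the same model, first events divided by subject-weeks at risk give a ratio of 1.00 whatever the stopping rates.

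**Random error.** The standard error of a difference at p = 0.30 is sqrt(0.21 × (1/75 + 1/20)) = 11.5 points, or sqrt(0.21 × (1/15 + 1/10)) = 18.7 points for a single starting-dose cell against its epoetin cell. That is at least three times the largest AE gap in the table (11.5/3.4).

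**The case against.** **The measure belongs to the SAP.** Exposure-adjusted rates are commonly specified there, and the protocol's wording does not exclude them. This stands: their absence from Section 11.7 is not an error in itself. What the protocol does fix is when observation ends and a default format that ignores its length.

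**Vadadustat must look safer than it is.** A reader might infer this, because vadadustat subjects change drug open-label while epoetin subjects stay on theirs. It is plausible, but the documents do not show it. The earlier study had no epoetin arm. Six of its seven withdrawals for worsening anemia were in the cohort started on TIW dosing, which no arm here starts on; the daily cohorts had 1 of 63. Dose adjustment also differs in this trial. If epoetin subjects stop more, the sign reverses.

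**Section 11.5 is contradicted.** A reader might set "It is expected that few subjects will discontinue Follow-Up" against 25 of 94. The sentence concerns leaving follow-up, and a subject who stops drug still attends Visits 14 and 15. Another study's completion rate does not contradict it.

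**Imbalance would be visible.** Disposition and reasons are tabulated by arm (Section 11.4), and AEs leading to discontinuation of drug have their own summary (Section 11.7). This helps a reader suspect the problem but does not adjust the percentages.

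**The gap is small beside the noise.** It is, and that limits how much weight the point can carry.

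**Conclusion.** The mechanism holds on the protocol's own text. AE reporting ends about four weeks after a permanent stop and scheduled Hb ends at EOT, while the stated summary is a crude percentage. Unequal stopping would understate harms in the arm that stops more. Where vadadustat stops at least as often, the range examined gives 0 to 3.4 points for a 30% AE and 0 to 4.1 points for a 30% scheduled-Hb event. With equal stopping nothing is lost, and the direction is not established. These sizes rest on assumed stopping rates, constant hazards that are equal in both arms, and the same event hazard on and after treatment.

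This is a worthwhile, low-cost improvement to a descriptive safety analysis. It is not evidence that the planned comparison favours vadadustat.

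**What to change.** In Section 11.7 (or the SAP), keep the counts and percentages and add, per arm, mean follow-up time and the rate of subjects with a first event per 100 subject-weeks at risk. Do this for AEs, SAEs, AEs of special interest and the Hb safety endpoints, with these rules:

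- Time at risk for treatment-emergent AEs covers the treatment-emergent window only.
- Post-treatment AEs are shown separately, because subjects who leave vadadustat go back to an ESA (Sections 8.4.12 and 9.3.4) and pooling would credit ESA time to vadadustat.
- Time at risk for Hb endpoints ends at the last Hb.

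The cost is about one sentence and added columns in the safety tables, from dates already collected. The rates assume a roughly constant hazard, are imprecise with 10 to 15 subjects per cell, and do not correct for informative stopping, so the crude counts stay beside them.

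Continuing AE review to Week 24 after a permanent stop is optional. It needs an amendment, and those events would be reported only as post-treatment. Section 11.5 needs no change on this account.
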